8.6 Adverse Events of Special Interest

Not applicable for this study.

9 STATISTICS

Complete details on the statistical methods for this study may be found in the Statistical Analysis Plan (SAP).

9.1 Sample Size

With a target sample size of 285 subjects in the safety analysis set and no events observed, the upper bound of a one-sided 95% confidence interval for zero observations is 0.01. Hence this sample size is large enough to rule out events that occur at rates greater than 1 case per 100 subjects.

In BHV3000-305 (C4951025) migraine-prevention study with EOD dosing, 73% of subjects in the rimegepant treatment group had ≥ 6 months (defined as ≥ 23 weeks) of double-blind or open-label rimegepant (i.e., 27% non-completion rate). In this study, it is expected that the 24-week non-completion rate will be higher due to early termination from baseline laboratory test

elevations. Assuming a 40% non-completion rate, approximately 170 subjects in the safety analysis set are expected to complete 24 weeks of treatment.

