5 POPULATION

5.1 Number of Subjects

A sufficient number of subjects will be screened to treat approximately 285 subjects with study drug to ensure that at least 170 subjects will complete 24 weeks of treatment. All subjects will be assigned to rimegepant 75 mg ODT dosed daily.

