1.2 Schedule of Analyses

There is 1 planned database lock, last subject last visit (LSLV) database lock, which occurs when the last subject completes the Follow-Up Week 8 Visit. The LSLV final CSR is produced after the LSLV database lock.

No interim analyses are planned.

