2.4 Protocol and Protocol Amendments

C4951011 SAP Versions 1 and 2 are based on C4951011 Protocol Version 3 (08-Mar-2022).

C4951011 SAP Version 3 is based on C4951011 Protocol Version 4 (07-Nov-2022). The target sample size was increased from 125 to 150 subjects to ensure that at least 100 subjects will complete 24 weeks of treatment.

C4951011 SAP Version 4 is based on C4951011 Protocol Version 5 (14-Feb-2023). The target sample size was increased from 150 to 170 subjects to ensure that at least 100 subjects will complete 24 weeks of treatment.

C4951011 SAP Version 5 is based on C4951011 Protocol Version 6 (07-Aug-2023). Protocol changes that affected statistical analyses were the following: changing the sponsorship to Pfizer; stating that there is 1 planned database lock; increasing the target sample size to 285 treated subjects to ensure that at least 170 subjects will complete 24 weeks of treatment; and modifying exclusion criteria, which affects relevant protocol deviations.

C4951011 SAP Versions 6 and 7 are based on C4951011 Protocol Version 6 (07-Aug-2023). These SAPs incorporate project-level changes to the Core SAP.

C4951011 SAP Version 8 is based on C4951011 Protocol Version 6 (07-Aug-2023). This SAP modifies relevant protocol deviations.

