5 SAMPLE SIZE, POWER, AND TYPE 1 ERROR

With a target sample size of 285 subjects in the safety analysis set and no events observed, the upper bound of a 1-sided 95% confidence interval (CI) for zero observations is 0.01. Hence, this sample size is large enough to rule out events that occur at rates greater than 1 case per 100 subjects.

In C4951025 (BHV3000-305) migraine-prevention study with every-other-day dosing, 73% of subjects in the rimegepant treatment group had \geq 6 months (defined as \geq 23 weeks) of double-blind or open-label rimegepant (i.e., 27% noncompletion rate). In this study, it is expected that the 24-week noncompletion rate will be higher due to early termination from baseline laboratory test elevations. Assuming a 40% noncompletion rate, approximately 170 subjects in the safety analysis set are expected to complete 24 weeks of treatment.

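### Zero events in 285 subjects gives an exact one-sided 95% upper bound of 1.05%, so the claim to exclude rates above 1 per 100 is not supported at guaranteed 95% confidence

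*Protocol*

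**What the plan says.** Protocol 9.1 takes 285 subjects in the safety analysis set and no events, and says that "the upper bound of a one-sided 95% confidence interval for zero observations is 0.01". It then draws the conclusion: "Hence this sample size is large enough to rule out events that occur at rates greater than 1 case per 100 subjects". SAP 5 gives the same bound ("the upper bound of a 1-sided 95% confidence interval (CI) for zero observations is 0.01") and the same conclusion ("Hence, this sample size is large enough to rule out events that occur at rates greater than 1 case per 100 subjects"). Neither section names the interval method, and both print the bound to two decimals.

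The number 285 also has a second basis. Protocol 9.1 continues: "Assuming a 40% non-completion rate, approximately 170 subjects in the safety analysis set are expected to complete 24 weeks of treatment". SAP 2.4 describes the latest change as "increasing the target sample size to 285 treated subjects to ensure that at least 170 subjects will complete 24 weeks of treatment". Protocol 5.1 treats the figure as approximate: "A sufficient number of subjects will be screened to treat approximately 285 subjects with study drug". The Synopsis and Protocol 1.5 give it as a maximum.

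**The concern.** The second sentence follows from the first only if the bound is at or below 1.000%. Printed as 0.01, the bound could lie on either side of that line. Under the exact method it lies just above, so rounding carries it across the limit that the next sentence says is met.

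This is a single-arm, descriptive safety study required after marketing approval, and this is the only statement about precision in the two documents. If a serious event type were not seen at all, a reader would take rates above 1 per 100 as excluded with 95% confidence, and the clinical study report could repeat that. The stake is the accuracy of that one statement. The choice of sample size and the planned tables do not depend on it.

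**Working it through.** **Inputs.** n = 285, zero events, one-sided 95% (α = 0.05) and the limit of 0.01 come from Protocol 9.1 and SAP 5. The 40% non-completion rate and about 170 completers come from the same sections. The interval method is not given, so several were tried.

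**1. The plan's own figure.** The exact (Clopper-Pearson) bound for zero events solves (1 − p)^n = 0.05:

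p = 1 − 0.05^(1/285) = 0.010456

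This rounds to 0.01, so the printed figure is reproduced.

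**2. The same bound by other methods.**

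| Method | Formula at 0/285 | Upper bound |
|---|---|---|
| Exact | 1 − 0.05^(1/285) | 1.046% |
| Poisson | −ln(0.05)/285 = 2.9957/285 | 1.051% |
| Rule of three | 3/285 | 1.053% |
| Wilson, one-sided | z²/(n + z²) = 2.7055/287.7055 | 0.940% |
| Mid-P | 1 − 0.10^(1/285) | 0.805% |
| Jeffreys | 95th percentile of Beta(0.5, 285.5) | 0.671% |

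The first four all print as 0.01 at two decimals, yet they lie on both sides of 1%. The printed figure therefore does not show which method was used.

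**3. Is a rate of 1% excluded?**

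P(0 events in 285, true rate 1%) = 0.99^285 = 0.0570

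This exceeds 0.05. The confidence is 1 − 0.0570 = 94.3%, and true rates from 1.00% to 1.046% stay inside the exact interval.

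**4. Do the approximate methods rescue the conclusion?** Coverage was computed at n = 285 by summing binomial probabilities over the outcomes whose bound is at or above the true rate. At a true rate of 1%, Wilson, mid-P and Jeffreys each miss only when zero events occur, so each covers 94.3%. The exact method covers more than 99.9%. Just above a method's own zero-event limit u, coverage is 1 − (1 − u)^285:

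- Wilson: 93.2%
- Mid-P: 90.0%
- Jeffreys: 85.3%

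**5. Does the looseness around 285 matter?**

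| Subjects treated | Exact bound |
|---|---|
| 280 | 1.064% |
| 285 | 1.046% |
| 290 | 1.028% |
| 298 | 1.0002% |
| 299 | 0.997% |

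ln(0.05)/ln(0.99) = 298.07, so 299 is the smallest number with an exact bound below 1%. That is 14 more than 285. If 285 is a maximum, the bound is 1.046% or higher.

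**6. The other basis for 285.** 285 × 0.60 = 171 completers, and 170/0.60 = 283.3. The completer target supports 285 without the zero-event argument.

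**The case against.** The strongest reply is that no printed number is wrong. The exact bound rounds to 0.01, and 1 per 100 is the same quantity at the same precision. The documents claim only a 95% interval, not guaranteed coverage, and one-sided Wilson is a recognised method that gives 0.94% and supports the conclusion as written. The exact method is also conservative. At a true rate of 1% it covers almost always, about 5 points above nominal, while Wilson is 0.7 points below. Averaged over true rates from 0.5% to 3%, coverage is 97.0% for Wilson, 95.8% for mid-P and 97.8% for exact, so Wilson and mid-P do not under-cover on average. The local lows in step 4 are their least favourable points. Finally, nothing in the plan uses the bound.

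Much of this stands. The figure 0.01 is correctly rounded, the choice of an exact method is a standard that the documents do not set, and the practical effect is very small. The conclusion itself remains undefended. It is stated as a threshold with no qualifier such as approximately, and it rests on an unnamed method. At the threshold itself, the methods that would support it fall short of 95%. For a statement that a rate has been excluded on safety grounds, guaranteed coverage is a reasonable standard.

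**Conclusion.** The concern holds, as a minor point. With 285 treated subjects and no events, the exact one-sided 95% upper bound is 1.046%, and a rate of 1% is excluded with 94.3% confidence. The excess over the stated limit is 0.05 percentage points. The error is in the inference from a rounded bound, not in the bound as printed.

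This rests on two assumptions: that an exclusion statement should use a method with at least 95% coverage, and that the number treated is close to 285. No test or decision rule uses the bound, and SAP 1.2 states: "No interim analyses are planned". The size of 285 is not in question.

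**What to change.** In SAP 5, replace the two sentences with: *If none of 285 treated subjects has the event, the exact (Clopper-Pearson) one-sided 95% upper confidence bound is about 1.05%, that is, 1.05 per 100 subjects.* Delete the claim that rates above 1 per 100 are excluded. If the number treated differs from 285, any statement of the bound should use the exact formula with the actual number.

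Make the same replacement in Protocol 9.1 at the next amendment. Protocol 12 requires an amendment with ethics approval for any permanent change, and this point does not justify one by itself.

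The cost is two sentences in each document and a slightly less favourable figure. Enrolment, design and planned tables do not change, and no separate bound for completers is needed.

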9.2 Analysis Sets

- Enrolled: Subjects who sign the informed consent form and are assigned a subject identification number.
- Safety: Subjects in the enrolled analysis set who take ≥ 1 dose of study drug (rimegepant).

9.3 Statistical Methods

Deaths will be listed without regard to onset for the enrolled analysis set.

The frequencies of the following on-treatment safety events and findings will be presented for the safety analysis set: AEs by intensity in $\geq 5\%$ of subjects (mild, moderate, severe, total); SAEs; AEs by relationship to study drug (related, possibly related, unlikely related, not related); AEs related to study drug by intensity; AEs leading to study drug discontinuation; hepatic-related AEs by intensity; hepatic-related AEs leading to study drug discontinuation; laboratory test abnormalities by toxicity grade; LFT elevations based on fold change above ULN; and vital sign, physical measurement, and ECG abnormalities. Frequencies of safety events will be based on the number and percentage of subjects with events.

The investigators will determine the intensity of AEs and the relationship of AEs to study drug. The investigators' terms will be coded using the latest version of the Medical Dictionary for Regulatory Activities (MedDRA). AEs will be presented by system organ class and preferred term. In tables by intensity, if a subject has an AE with different intensities over time, then only the greatest intensity will be reported. In tables by relationship to study drug, if a subject has an AE with different relationships over time, then the highest degree of relatedness to study drug will be reported.

Laboratory test results will be graded according to numeric laboratory test criteria in Common Terminology Criteria for Adverse Events (CTCAE) Version 5.0 (2017), if available. Otherwise, if CTCAE grades are not available, then results will be graded according to numeric laboratory test criteria in Division of AIDS (DAIDS) Table for Grading the Severity of Adult and Pediatric Adverse Events Corrected Version 2.1 (2017). If a subject has a laboratory test abnormality with different toxicity grades over time, then only the highest toxicity grade will be reported.

In addition, Quality Tolerance Limits (QTLs) are predefined parameters that are monitored during the study. Important deviations from the QTLs and any remedial actions taken will be summarized.

9.4 Schedule of Analyses

There is 1 planned database lock which will occur after the last subject completes the Follow-up Week 8 Visit. The final clinical study report (CSR) will be produced to support regulatory requirements after the final database lock.

10 ETHICS AND RESPONSIBILITIES

10.1 Good Clinical Practice

This study will be conducted in compliance with the protocol, Good Clinical Practice (GCP), Good Laboratory Practice (GLP), International Conference on Harmonization guidelines, and all applicable regulations, including the Federal Food, Drug and Cosmetic Act, U.S. applicable Code of Federal Regulations (title 21), any Independent Ethics Committee (IEC) requirements relative to clinical studies. The study will also be conducted in compliance with the recommendations laid down in the most recent version of the Declaration of Helsinki.

This study will be conducted in compliance with the protocol. The protocol and any amendments and the subject informed consent will receive Institutional Review Board/Independent Ethics Committee (IRB/IEC) approval/favorable opinion prior to initiation of the study.

The Sponsor is responsible for ensuring that all updated relevant information related to the protocol be submitted to regulatory authorities and Independent Ethics Committees in accordance with local laws and regulations. This includes expedited reporting of suspected unexpected serious adverse reactions per regulatory guidelines.

All serious breaches must be reported to Pfizer (or designee) immediately. A Serious breach is a breach of the conditions and principles of GCP in connection with the study or protocol, which is likely to affect, to a significant degree, the safety or physical or mental integrity of the subjects of the study or the scientific value of the study.

Study personnel involved in conducting this study will be qualified by education, training, and experience to perform their respective task(s).

This study will not use the services of study personnel where sanctions have been invoked or where there has been scientific misconduct or fraud (e.g., loss of medical licensure, debarment).

It is the Sponsor's responsibility to submit the protocol and its amendments (if any), and the ICFs to regulatory authorities when necessary.

10.2 Data and Safety Monitoring Committee

This study will not make use of a Data Safety Monitoring Committee (DSMC). The study drug rimegepant has been tested and found to be well tolerated. Safety will be closely monitored via oversight by the investigators, Sponsor and CRO/designee and an Institutional Review Board/Independent Ethics Committee.

10.3 Institutional Review Board/Independent Ethics Committee

The Investigators agree to provide the IRB/IEC with all appropriate documents, including a copy of the protocol/amendments, ICFs, advertising text (if any), Investigator's brochure (if any) and any other written information provided to study subjects. The trial will not begin until the Investigators have obtained the IRB/IEC favorable written approvals for the above-mentioned study documents.

In the event that the protocol is amended, the revised protocol must be approved by the IRB/IEC prior to its implementation, unless the changes involve only logistical or administrative aspects of the trial.

10.4 Informed Consent

Investigators must ensure that subjects, or, in those situations where consent cannot be given by subjects, their legally acceptable representatives, are clearly and fully informed about the purpose, potential risks, and other critical issues regarding clinical studies in which they volunteer to participate.

Pfizer (or designee) will provide the investigator with an appropriate (i.e., Global or Local) sample informed consent form which will include all elements required by ICH, GCP and applicable regulatory requirements. The sample informed consent form will adhere to the ethical principles that have their origin in the Declaration of Helsinki.

Before the potential subject has undergone any study-related screening procedures, the nature of the study and the potential risks associated with it will be explained to the subject, and the subject will be given an opportunity to ask questions to his or her satisfaction. After the questions are answered, but before proceeding further, if the subject has not opted out of the CTSdatabase portion of the study, they must sign and date an IRB/IEC approved written informed consent form for study participation and CTSdatabase participation. The signed and dated ICF will be retained at the Investigator's site, with a copy provided to the study subject and date will be entered in his or her CRF or appropriate system. The IRB/IEC must review and approve all protocol versions and informed consent form versions and a copy of each version of the IRB/IEC approved protocol and informed consent form is to be retained in the Study Master file. Any revisions to the protocol or ICF will be reviewed and approved by the IRB/IEC and subjects will be informed of ICF changes and document continuing consent by signing and dating the revised version of the ICF.

If a revised ICF is introduced during the study, each subject's further consent must be obtained. The new version of the ICF must be approved by the IRB/IEC, prior to subsequently obtaining each subject's consent.

If informed consent is initially given by a subject's legal guardian or legally acceptable representative, and the subject subsequently becomes capable of making and communicating their informed consent during the study, then the consent must additionally be obtained from the subject.

The informed consent form must also include a statement that Pfizer and its representatives and regulatory authorities may have direct access to subject records.

10.5 Case Report Forms

An Investigator is required to prepare and maintain adequate and accurate case histories designed to record all observations and other data pertinent to the investigation of each study subject. Data reported on the CRF that are derived from source documents must be consistent with the source documents or the discrepancies must be explained.

Electronic CRFs will be prepared for all data collections fields when electronic data capture (EDC) is being used.

The confidentiality of records that could identify subjects must be protected, respecting the privacy and confidentiality rules in accordance with the applicable regulatory requirement(s).

The Investigator must retain a copy of the CRFs including records of changes and corrections. If EDC is being used, signatures will be obtained electronically and a copy of the electronic CRFs will be provided (or the data from the CRFs) for future reference.

10.6 Dissemination of Clinical Study Data

Pfizer fulfills its commitment to publicly disclose clinical study results through posting the results of studies on www.clinicaltrials.gov (ClinicalTrials.gov), the EudraCT/CTIS, and/or [www\(pfizer.com](http://www(pfizer.com), and other public registries and websites in accordance with applicable local laws/regulations. In addition, Pfizer reports study results outside of the requirements of local laws/regulations pursuant to its SOPs.

In all cases, study results are reported by Pfizer in an objective, accurate, balanced, and complete manner and are reported regardless of the outcome of the study or the country in which the study was conducted.

www.clinicaltrials.gov

Pfizer posts clinical trial results on www.clinicaltrials.gov for Pfizer sponsored interventional studies (conducted in patients) that evaluate the safety and/or efficacy of a product, regardless of the geographical location in which the study is conducted. These results are submitted for posting in accordance with the format and timelines set forth by US law.

EudraCT/CTIS

Pfizer posts clinical trial results on EudraCT/CTIS for Pfizer sponsored interventional studies in accordance with the format and timelines set forth by EU requirements.

[www\(pfizer.com](http://www(pfizer.com)

Pfizer posts CSR synopses and plain-language study results summaries on [www\(pfizer.com](http://www(pfizer.com) for Pfizer sponsored interventional studies at the same time the corresponding study results are

posted to www.clinicaltrials.gov. CSR synopses will have personally identifiable information anonymized.

Documents within marketing applications

Pfizer complies with applicable local laws/regulations to publish clinical documents included in marketing applications. Clinical documents include summary documents and CSRs including the protocol and protocol amendments, sample CRFs, and SAPs. Clinical documents will have personally identifiable information anonymized.

10.6.1 Data sharing

Pfizer provides researchers secure access to subject level data or full CSRs for the purposes of “bonafide scientific research” that contributes to the scientific understanding of the disease, target, or compound class. Pfizer will make data from these trials available 18 months after study completion. Subject level data will be anonymized in accordance with applicable privacy laws and regulations. CSRs will have personally identifiable information anonymized.

Data requests are considered from qualified researchers with the appropriate competencies to perform the proposed analyses. Research teams must include a biostatistician. Data will not be provided to applicants with significant conflicts of interest, including individuals requesting access for commercial/competitive or legal purposes.

10.7 Sponsor's Medically Qualified Individual

The contact information for the sponsor's MQI for the study is documented in the study contact list located in the principal investigator ISF.

To facilitate access to their investigator and the sponsor's MQI for study related medical questions or problems from non-study healthcare professionals, subjects are provided with an ECC at the time of informed consent. The ECC contains, at a minimum, (a) protocol and study drug identifiers, (b) subject's study identification number, (c) site emergency phone number active 24 hours/day, 7 days per week, and (d) Pfizer Call Center number.

The ECC is intended to augment, not replace, the established communication pathways between the subject and their investigator and site staff, and between the investigator and sponsor study team. The ECC is only to be used by healthcare professionals not involved in the research study, as a means of reaching the investigator or site staff related to the care of a subject. The Pfizer Call Center number is to be used when the investigator and site staff are unavailable. The Pfizer Call Center number is not for use by the subject directly; if a subject calls that number directly, they will be directed back to the investigator site.

